8.2.4. Vital Signs

Body temperature, pulse rate, respiratory rate, and supine blood pressure will be assessed before blood collection for laboratory tests.

Supine blood pressure and pulse rate measurements will be assessed once with a completely automated device. Manual techniques will be used only if an automated device is not available.

Blood pressure and pulse rate measurements should be preceded by at least 5 minutes of rest for the participant in a quiet setting without distractions (eg, television, cell phones).

O₂ saturation will only be measured before the start of the IP infusion and during the inpatient stay post IP administration (see [Sections 1.3.1](#) and [Section 1.3.2](#)).

8.2.5. Electrocardiograms

A single 12-Lead ECG will be collected using an ECG machine, provided by the Sponsor, that automatically calculates the heart rate and measures PR, QT, corrected QT (QTc) intervals and QRS complex. The Fridericia corrected QTc (QTcF) will be the basis for safety monitoring of QT intervals. All scheduled ECGs should be performed after the participant has rested quietly for at least 10 minutes in the supine position. ECG data will be submitted to a central laboratory for measurement and interpretation and will also be reviewed at the site for safety monitoring.

If a post-dose QTcF interval remains ≥ 30 msec from the baseline **and** is > 450 msec; or b) an uncorrected QT or QTcF value is ≥ 500 msec for any scheduled ECG for greater than 4 hours (or sooner, at the discretion of the Investigator), or if QTcF intervals get progressively longer, the participant should undergo continuous ECG monitoring. A cardiologist should be consulted if QTc intervals do not return to less than the criteria listed above after 8 hours of monitoring (or sooner, at the discretion of the Investigator).

The final ECG report from the central laboratory should be maintained in the participant's source documentation as well as the final interpretation of the ECG recording. Any clinically significant changes from the Screening ECG may potentially be AEs ([Appendix 7](#)) and should be evaluated further, as clinically warranted.

If the leads are placed incorrectly on the participant's limbs, the ECG should be repeated. It is important that leads be placed in the same and correct positions each time in order to achieve precise ECG recordings. If a machine-read QTc value is prolonged, the Fridericia QT correction should be obtained to interpret whether a safety event has occurred as defined above.

ECG values of potential clinical concern are listed in [Appendix 7](#).

8.2.6. Echocardiogram

Echocardiograms will be collected and read locally for immediate interpretation and safety monitoring and will be submitted to a central laboratory for standardized interpretation.

To ensure safety of the participants, a qualified individual at the site will evaluate the echocardiogram at least for left ventricular ejection fraction (LVEF), but other parameters may also be assessed, including but not limited to myocardial strain. Echocardiogram should be performed using a 2-D imaging collection method.

If the LVEF is below 50% on the echocardiogram at any visit after screening, the participant should be referred to a cardiologist for further assessment.

8.2.7. Cardiac Troponin I

[figure not shown]
To monitor for cardiac injury, cTn-I will be assessed. If a local laboratory cannot perform the cTn-I assay, cTn-T can be substituted for the local laboratory assessments.

If a participant presents with a Screening cTn-I value $>3 \times 99^{\text{th}}$ percentile the following instructions should be followed:

- Perform clinical evaluation for cardiac signs or symptoms;
- Review Screening ECG for significant findings suggestive of ischemia;
- If either of the above is positive, repeat cTn-I approximately 48 to 96 hours after the first blood draw and request a cardiology consult.

The algorithm in Figure 3 provides instructions for the management of elevated cTn-I (or cTn-T) values during the course of the study, after the Screening visit.

Figure 3. Management of Elevated Cardiac Troponin I (cTn-I)/Cardiac Troponin T (cTn-T) values

*Results of cTn-I should only be compared to results of cTn-I and results of cTn-T should only be compared to results of cTn-T.

†Echocardiogram and NT-ProBNP/BNP are required only during the first 14 days post IP administration.

‡ECG, echocardiogram, and cardiac MRI (original and follow-up scans) performed during the evaluation of an elevated cardiac troponin value must be read locally for immediate interpretation and safety monitoring and will be submitted to a central reader as soon as possible (i.e., in less than 72 hours) for standardized interpretation. For events of elevated troponin or myocarditis with or without abnormal findings in the initial cardiac MRI, a follow up cardiac MRI will be performed approximately 3 months after the start of the event. This cardiac MRI will be reviewed at the site for safety monitoring and will also be submitted to the imaging CRO for measurement and interpretation as soon as possible (i.e., in less than 72 hours).

Sites will repeat troponin and NT-ProBNP tests (or BNP, if NT-ProBNP is not available) approximately every 48-72 hours until each test returns to Baseline values or reaches a level considered not clinically significant by the investigator.

NOTE: If at any time during the study a participant presents with a cTn-I value >3 x 99th percentile and he had not been previously evaluated, the instructions for evaluation outlined in the algorithm should be followed.

8.2.8. Cardiac MRI

Cardiac MRI will be performed using a 1.5T or 3.0T scanner with an appropriate coil for cardiac imaging. The scan may include imaging before and after IV administration of a gadolinium-based contrast agent. Sites will be responsible for confirming participant eligibility to undergo MRI scanning and gadolinium contrast administration. If the site

considers gadolinium contrast administration unsafe, or if the participant has a history of allergy to gadolinium, cardiac MRI without contrast administration will be performed.

Complete details on the cardiac MRI acquisition protocol, image quality review, and transmission of data to the imaging contract research organization (CRO) will be provided in an Imaging Manual offered to the study sites. The imaging CRO will include central review of all cardiac MRI scans. The central reviewer analysis will include, at a minimum, evaluation of LVEF, myocardial fibrosis as measured by late gadolinium enhancement (LGE) if gadolinium is used, and evaluation of myocardial strain. Cardiac MRIs (original and any follow-up scans) performed due to an acute event, as per [Section 8.2.7](#), will be submitted to the imaging CRO for measurement and interpretation as soon as possible (i.e., in less than 72 hours), and will also be reviewed at the site for safety monitoring. For events of elevated troponin or myocarditis with or without abnormal findings in the initial cardiac MRI, a follow up cardiac MRI will be performed approximately 3 months after the start of the event. This cardiac MRI will be reviewed at the site for safety monitoring and will also be submitted to the imaging CRO for measurement and interpretation as soon as possible (i.e., in less than 72 hours).

8.2.8.1. Management of Incidental Findings

An incidental finding is one unknown to the participant that has potential health or reproductive importance, which is discovered unexpectedly in the course of a research study, but is unrelated to the purpose and beyond the aims of the study.

Cardiac MRI images will be reviewed by the central review facility. The purpose of this review is to evaluate images for LVEF, LGE, and strain over time. Central image review is not a complete medical review of the participant. If, during the central review process, an unexpected observation is identified and this finding could, in the opinion of the central reviewer, have a significant health or reproductive consequence, this finding may be shared with the study sponsor for disclosure to the investigator. All follow-up testing and final diagnosis will be left to the discretion of the medical professionals at the site or those with an existing physician participant relationship. The investigator will be responsible for reporting any AEs identified from incidental findings as described in the AE reporting section. Identification of such incidental findings during the central review process should not be expected, and the site maintains responsibility for performing a general safety review of all images in accordance with site protocols.

8.2.9. Clinical Safety Laboratory Assessments

See [Appendix 2](#) for the list of clinical safety laboratory tests to be performed and the [SoA](#) for the timing and frequency.

The Investigator or their designee must review the laboratory report, document this review, and record any clinically relevant changes occurring during the study in the AE section of the CRF. Clinically significant abnormal laboratory findings are those which are not associated with the underlying disease, unless judged by the Investigator to be more severe than expected for the participant's condition.

All laboratory tests with values considered clinically significantly abnormal during participation in the study should be repeated until the values return to normal or baseline or are no longer considered clinically significant by the Investigator or medical monitor.

If such values do not return to normal/baseline within a period of time judged reasonable by the Investigator, the etiology should be identified and the Sponsor notified.

All protocol-required laboratory assessments, as defined in [Appendix 2](#), must be conducted in accordance with the laboratory manual and the [SoA](#).

8.2.10. Post IP Intensified Safety Monitoring (at Year 1 and Year 2)

Due to the potential for an immune reaction against the AAV9 vector and/or the transgene, participants will undergo an intensified safety monitoring period for the first 34 days after IP administration in Year 1 and in Year 2.

Following IP administration, participants will be monitored as inpatients for 7 days, or longer, if deemed necessary by the Investigator (see [SoA](#) for details). Participants must be in an individual room, ie, not shared with other patients. Following IP administration, it is recommended that the IV line remains for at least 48 hours in case IV hydration or treatment is necessary due to nausea, vomiting, anorexia, etc. Once the IV line is removed, volume status should be assessed regularly, and if a participant subsequently experiences nausea or vomiting, consideration should be given to the placement of an IV line for treatment with an IV anti-emetic, hydration and replacement of the oral protocol-mandated glucocorticoid regimen by an IV regimen (see [Section 6.5.1](#)). Upon discharge, participants will be asked to stay local to the site (ie, if they do not live near the site, they will be asked to stay in at an overnight facility) through Day 14 after Year 1 and Year 2 IP administration, or longer, if deemed necessary by the Investigator. If adverse events possibly related to IP administration are observed, participants should not be discharged until the events have resolved.

Once enrollment is complete and the last participant has completed 14 days post Year 1 IP administration, the E-DMC will review the safety information accrued to determine if any changes to the Year 2 IP administration schedule, including need for and length of hospitalization, are required.

During the first 34 days post IP administration participants will undergo study visits on:

- Year 1: Day 2 (Visit 4), Day 4 (Visit 5), Days 6-10 (Visits 6-10), Day 14 (Visit 11), Day 21 (Visit 12, a remote visit is allowed) and Day 34 (Visit 13), for clinical and laboratory assessments.
- Year 2: Day 2 (Visit 21), Day 4 (Visit 22), Days 6-10 (Visits 23-27), Day 14 (Visit 28), Day 21 (Visit 29, a remote visit is allowed) and Day 34 (Visit 30), for clinical and laboratory assessments. Cohort 1 participants confirmed to meet exclusion criterion 15 and participants who declined Year 2 IP administration will not attend these visits (see [Section 1.3.2](#) footnote “bb”, and [Appendix 12](#)).

Local Laboratory Assessments

- On Visit 2 and Visits 4 to 10 (Day 2 to 10) at Year 1, and Visits 20 to 27 (Days 1 to 10) at Year 2, the sites will perform blood and urine safety tests at their local laboratories. This will ensure a very rapid turnaround (within 1 to 2 hours) and review of the results during a period that is critical for the detection of immune mediated-adverse events.
- When copies of medical records including local laboratory reports are provided to Pfizer for the purpose of critical safety review, all participant identifiers, with the exception of the participant number, must be redacted on the copies of the medical records before submission to Pfizer. The files should be password-protected.

Participants and their caregivers will be instructed to carefully monitor the liquid intake and urinary output of the participants for the first 34 days post IP administration (see [Section 5.5.2](#) for additional details). Participants will be required to return to the site for evaluation by the Investigator or designated medically qualified individual, within 24 hours if any of the following occur:

- No urine output for 12 hours, or a significant change in urine output in less than 24 hours, or observation of tea-colored urine;
- Evidence of significant reduction in estimated glomerular filtration rate, determined by clinically relevant increases in serum cystatin C or serum creatinine (eg, doubling) from value at the Screening Visit (central laboratory) or from value at the Baseline Visit (local laboratory) at Year 1 or from Visit 19 at Year 2;
- Clinically relevant increase from Screening value in hematocrit or hemoglobin;
- Presence of anion gap acidosis;
- Abnormality on blood smear, or haptoglobin <LLN or reduced to <50% from Screening value (indicating unequivocal hemolysis);
- Platelets $<75 \times 10^3/\mu\text{l}$.

Hospital admission and/or treatment with eculizumab, as per [Section 6.5.1](#), or additional immunosuppression may be warranted, at the discretion of the Investigator and/or Sponsor.

Since admission to the intensive care or coronary unit is a possibility which could involve placement of a central catheter and/or an endomyocardial biopsy to aid diagnosis and management, and/or mechanical circulatory and/or respiratory support, investigators should discuss the possibility of these interventions with the pediatric cardiologist (sub-investigator). These measures should be discussed with participants and caregivers during the review of the ICD.

Investigators in Japan should see [Section 10.10 \(Appendix 10\)](#) for details on the management of the participants during the first 14 days post IP administration.

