6.3.3. Sensitive Clinical Data

Select safety and immunogenicity results

In order to prevent the functional unblinding of the treatment assignment, the results of the following assessments will not be shared with the study team or the site after Year 1 IP administration and throughout the blinded portion of the study:

- CK;
- AST and ALT;
- NAb to AAV9 (See [Section 7.1](#));
- ELISpot to AAV9 and mini-dystrophin;
- ADA to AAV9 and mini-dystrophin;
- C3 and C4.

An unblinded medically qualified monitor (medical monitor) will review the results of CK, AST and ALT, NAb to AAV9, and ADA to mini-dystrophin for each participant on an ongoing basis and will decide if any result(s) should be repeated and/or shared with the site and the study team, due to a judgement that the results could reflect a safety issue (eg, liver injury, myositis, other immunological reaction).

If a participant in Cohort 2 presents with a positive test for NAb to AAV9 on the sample taken at the Day 34 (Visit 13) he will be withdrawn from the study given that it would already be determined at that time that he is not be eligible for fordadistrogene movaparvovec administration at Year 2. If this situation occurs while the study is still accruing participants, an additional 2 participants may be randomized for each Cohort 2 participant who is withdrawn.

Additionally, if the threshold of laboratory abnormalities for a potential drug-induced liver injury (DILI) case has been met (see [Appendix 6](#)), the results for ALT and AST will be shared with the site and the study team until the potential DILI has been investigated and it is considered resolved.

If a clinical event occurs that, in the opinion of the Sponsor and/or the Investigator, could be due to an immunological reaction, additional ad-hoc assessments of NAb to AAV9, ADA to AAV9 and mini-dystrophin, ELISpot to AAV9 and mini-dystrophin may be conducted if

considered indicated by the Sponsor and/or the Investigator for the interpretation and/or the management of the immunological reaction. The results of these tests will be shared with the site and the study team.

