Additionally, to further prevent the introduction of bias in the scoring of the functional assessments, all possible measures should be put into place to prevent the clinical evaluators from viewing the participants' medical records/database where relevant information that could lead to functional unblinding, such as the occurrence of lab abnormalities or AEs/SAEs, may be recorded.

Viral vector shedding results

In order to prevent the functional unblinding of the treatment assignment, the results of the following assessments will not be shared with the site or the study team throughout the blinded portion of the study:

- Viral vector shedding.

An unblinded qualified Sponsor representative, independent and firewalled from the study team, will review the viral vector shedding results for each participant on an ongoing basis. The unblinded qualified Sponsor representative will communicate to the site when sampling in a given matrix (ie, blood, urine, or saliva) for each participant can be stopped. For Cohort 1 participants sampling for each matrix will be stopped when two consecutive samples test negative. To prevent unblinding, sampling will also be stopped for a matched Cohort 2 participant.

Muscle biopsy results

In order to prevent the functional unblinding of the treatment assignment, the results of the following assessments will not be shared with the site or the study team throughout the blinded portion of the study:

- Percent normal mini-dystrophin expression level, quantified by LC-MS.
- Percent of muscle fibers expressing mini-dystrophin, assessed by immunohistochemistry.

No review of these results will be conducted by the unblinded medical monitor.

Year 2 IP eligibility laboratory results

Given that the below eligibility assessment does not apply to Cohort 1 for Year 2 IP administration and in order to prevent unblinding of the treatment assignment, when assessing Cohort 2 participants' eligibility for Year 2 IP administration, the following test

results will not be shared with the sites and the study team, and will only be reviewed by an unblinded medical monitor (see [Section 7.1](#)).

- Laboratory results at Day 360 (Visit 19):

 NAb to AAV9;

 Absolute neutrophil count <1000 cells/mm³;

 Platelets <150 x 10³/µl;

 Cystatin C >1.2 x ULN;

 Positive hepatitis A virus (anti-HAV) immunoglobulin M, hepatitis B surface antigen (HbsAg), and/or hepatitis C antibody (HCVAb);

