Cohort 1 participants confirmed to meet exclusion criterion 15 and participants who declined Year 2 IP administration will not receive their protocol-mandated glucocorticoid regimen in Year 2 and will continue receiving their background glucocorticoid treatment during Year 2, see [Appendix 12](#) and [Section 7.2.1](#).

Participants with delayed Year 2 IP administration will not receive their protocol-mandated glucocorticoid regimen until the pause is lifted and Year 2 IP administration takes place; they will remain on their background glucocorticoid regimen until then, see [Section 5.3.2](#).

Eculizumab

Treatment with one or more doses of the complement inhibitor, eculizumab, should be considered by the Investigator, according to the local prescribing information, for any participant who presents with a clinical picture of complement-mediated thrombotic microangiopathy. Signs consistent with atypical hemolytic uremic syndrome (aHUS) that would indicate the need for treatment include:

1. Creatinine $>2 \times$ Screening value; OR
2. Platelets $<75 \times 10^3/\mu\text{l}$ AND either (a) or (b):
 - a. Evidence of hemolysis:
 - Haptoglobin $<\text{LLN}$ or reduced to $<50\%$ from Screening value (Year 1) or from Visit 19 value (Year 2); or
 - Schistocytes on blood smear.
 - b. Evidence of nephropathy:
 - Anuria >12 hours; or
 - $\geq 2+$ blood or protein on urine dipstick; or
 - An increase of $>50\%$ in serum creatinine from Screening value.

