7. DISCONTINUATION OF STUDY INTERVENTION AND PARTICIPANT DISCONTINUATION/WITHDRAWAL

7.1. Discontinuation of Study Intervention

In the context of this study, treatment will consist of two single intravenous infusions, one of fordadistrogene movaparvovec and one of placebo (Section 4.1). Following IP administration on Day 1 (Visit 3), the only potential for discontinuation of study intervention is at the time of IP administration in Year 2. Cohort 1 participants will receive placebo on Day 390 (Visit 20) and will not be discontinued from study intervention although the timing of IP administration may be affected by eligibility criteria, as described below, in order to preserve the blinding of the ongoing study. Cohort 2 participants are scheduled to receive fordadistrogene movaparvovec one year after receiving placebo if they remain eligible for Year 2 IP administration. Participants in Cohort 2 who are determined to be ineligible to receive fordadistrogene movaparvovec by the criteria listed below (1-6) will discontinue study intervention.

Cohort 2 participants will be confirmed to be eligible for Year 2 IP administration before receiving treatment with fordadistrogene movaparvovec. There are no eligibility criteria for Cohort 1 participants for Year 2 IP administration based on the results of hematology and chemistry profiles or of results of testing for NAb to AAV9, but they will be reviewed for safety reasons. In order to preserve the blinding of the ongoing study, an unblinded, medically qualified monitor (medical monitor), independent from the team conducting and monitoring the study, will be the only person to review the results of the hematology and chemistry profiles as well as of the NAb to AAV9. These laboratory results will be blinded to the site and the Sponsor.

Additionally, the unblinded medical monitor will determine if any test(s) should be repeated (due to a result outside of allowable limits for Year 2 IP administration eligibility considered possibly transient for Cohort 2 participants, and/or due to test showing a potential safety issue considered possibly transient for Cohort 1 and Cohort 2 participants). The unblinded medical monitor will also decide if any result(s) must be unblinded to the site and the Sponsor, in the unlikely event that it reflects a safety issue.

Cohort 2 participants will not be eligible for Year 2 IP administration if they present with any of the following:

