1. Positive test for NAb to AAV9, based on the threshold determined by the Central Laboratory, at Day 360 (Visit 19). If the time between Day 360 (Visit 19) and Day 390 (Visit 20) is more than 55 days, a second NAb to AAV9 test must be performed and confirmed to be negative before Year 2 IP administration. Dosing cannot occur unless there is a negative NAb to AAV9 test from a sample collected 55 or less days before the day of IP administration, as reviewed by the unblinded medical monitor.
2. Abnormality in hematology or chemistry profiles at Day 360 (Visit 19). A single repeat for value(s) outside allowable limits is permitted to re-assess eligibility:
 - Absolute neutrophil count <1000 cells/mm³;
 - Platelets <150 x 10³/μl;
 - Cystatin C >1.2 x ULN;

Positive hepatitis A virus (anti-HAV) immunoglobulin M, hepatitis B surface antigen (HbsAg), and/or hepatitis C antibody (HCVAb);

Markers of hepatic inflammation or overt or occult cirrhosis as evidenced by one or more of the following:

 - PT > ULN; prolonged INR >ULN;
 - GLDH >2 x ULN;
 - Total bilirubin >1.5 x ULN (unless the participant has a history of Gilbert disease) and direct bilirubin >0.5 mg/dL;
 - GGT >1.5 x ULN.

Additionally, the unblinded medical monitor will confirm the treatment allocation for participants with the conditions listed below, so those participants in Cohort 2 who meet any of these conditions do not receive Year 2 IP administration and are withdrawn from the study:

3. Participants screened or randomized who had not yet received Year 2 IP administration and were retrospectively confirmed to meet exclusion criterion 15 (see [Appendix 12](#)).
4. LVEF <50% on echocardiogram performed at Day 360 (Visit 19), or at the unplanned visit to re-assess eligibility for Year 2 IP administration.

5. Diagnosis of current or prior myocarditis by a pediatric cardiologist.
6. Not a candidate for mechanical cardiac or respiratory support, or any other invasive intervention, if indicated for management of an acute event as determined by the cardiologist in consultation with the investigator.

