Cohort 1 participants, as confirmed by the unblinded medical monitor, will not receive Year 2 IP administration, placebo, if they meet exclusion criterion 15. They will not require post-IP safety monitoring in Year 2, will not attend Visit 18 in Year 1 and Visits 20 to 30.2 in Year 2, and will not receive their protocol-mandated glucocorticoid regimen in Year 2. These participants will remain in the study for safety monitoring as described in [Appendix 12](#).

Once the unblinded medical monitor has communicated to the Investigator that the participant meets eligibility criteria based on laboratory tests and echocardiographic results, then the Investigator will ensure that none of the criteria listed below are met before allowing IP administration.

To preserve the blinding of the treatment assignment for the site and for the Sponsor, the following criteria will be assessed for both Cohort 1 and Cohort 2 participants.

7. Receipt of a live attenuated vaccination within 90 days prior to Day 390 (Visit 20). If a participant has received a live attenuated vaccination within 90 days prior to Day 390 (Visit 20), IP administration must be delayed until at least 90 days after the last administration of the vaccine.
8. Receipt of an inactivated vaccine (eg, influenza, meningococcal, pneumococcal, *Haemophilus influenzae* vaccination) within 30 days prior to Day 390 (Visit 20). If a participant has received an inactivated vaccine within 30 days prior to Day 390 (Visit 20), IP administration must be delayed until at least 30 days after the last administration of the vaccine.
9. Receipt of an mRNA or DNA-based, or non-replicating viral vector vaccine (eg, against SARS-CoV2) within 30 days of Day 390 (Visit 20). If a participant has received any of the above-listed vaccines within 30 days prior to Day 390 (Visit 20), IP administration must be delayed until at least 30 days after the last administration of the vaccine.
10. Receipt of any systemic immunosuppressant agents other than glucocorticoids, and/or systemic antiviral therapy, and/or interferon. If a participant has received any of these therapies, IP administration must be delayed until at least 30 days after the last dose.
11. Acute infection at Day 360 (Visit 19) that, in the judgement of the Investigator, is not expected to be fully resolved at least 14 days prior to IP administration on Day 390 (Visit 20).

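### Section 8.2.10 judges a Year 2 rise in cystatin C against Visit 19, a value that Sections 6.3.3 and 7.1 withhold from the site, and no one is assigned the comparison

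*Protocol*

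**What the plan says.** Section 8.2.10 sets a 34-day intensified monitoring period after each infusion and lists findings that bring the boy back within 24 hours. One is evidence of reduced glomerular filtration, shown by a clinically relevant increase in cystatin C or creatinine, with doubling as an example. The references are Screening for the central laboratory, and then "from value at the Baseline Visit (local laboratory) at Year 1 or from Visit 19 at Year 2".

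Section 6.3.3, under the Year 2 eligibility laboratory results, lists Day 360 (Visit 19) results including cystatin C and says these "results will not be shared with the sites and the study team, and will only be reviewed by an unblinded medical monitor". Section 7.1 says of the hematology and chemistry profiles and the NAb result: "These laboratory results will be blinded to the site and the Sponsor". Criterion 2 of that section places cystatin C within those profiles ("Cystatin C >1.2 x ULN"). The monitor may unblind a result that reflects a safety issue. Otherwise the site receives only the outcome: "Once the unblinded medical monitor has communicated to the Investigator that the participant meets eligibility criteria based on laboratory tests and echocardiographic results", the investigator goes on to the remaining criteria.

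Outside the eligibility check, Section 6.3.3 says that the monitor "will review the results of CK, AST and ALT, NAb to AAV9, and ADA to mini-dystrophin for each participant on an ongoing basis". Cystatin C is not in that list.

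**The concern.** A stated safety rule points to a number that another stated rule hides from the people who must apply it. Post-dose cystatin C is not on the sensitive-data list, so the site sees the later value but not the reference it is told to use. The monitor holds the reference but is not asked to compare.

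The timing gives this some weight. Cohort 2 first receives the vector in Year 2. The protocol's clinical overview reports two serious events in the Phase 1b study, consistent with atypical hemolytic uremic syndrome and including reversible nephropathy, within two weeks of infusion. Cystatin C is also the renal marker the sponsor chose for eligibility, at both Screening and Visit 19. If the named reference is unavailable, sites will pick their own or pass over the cystatin C limb, and they may not all do the same.

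**Working it through.** The protocol gives no figure to reproduce. The check sets the sections side by side and counts visits.

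**Which reference applies in Year 2.** The sentence in Section 8.2.10 ties Visit 19 to Year 2. Section 6.5.1 uses the same pairing for haptoglobin: "from Screening value (Year 1) or from Visit 19 value (Year 2"). That makes Visit 19 the natural Year 2 reference.

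**Is that value available to the site?**
- Section 6.3.3 introduces its list in the context of assessing eligibility, but says nothing about releasing the values afterwards.
- Section 7.1 states the blinding without a time limit.
- Appendix 2, Table 3, footnote f treats Day 360 neutrophils and platelets, two other analytes on the same list, as withheld results, also without a time limit.
- The release route in Section 7.1 covers a result that itself signals a safety issue. An unremarkable Visit 19 cystatin C, which is the usual reference, would not qualify.

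**Is anyone else given the comparison?** The monitor's ongoing review covers CK, AST and ALT, NAb and ADA to mini-dystrophin. No section shown adds cystatin C.

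**How many panels are involved.** Cystatin C belongs to the central clinical safety panel (Appendix 2, Table 3, column headed Other). Section 8.2.10 gives the later Year 2 visits as "Day 14 (Visit 28), Day 21 (Visit 29, a remote visit is allowed) and Day 34 (Visit 30"). With Year 2 Day 1 at Day 390:
- Day 14 is 390 + 13 = Day 403
- Day 21 is 390 + 20 = Day 410
- Day 34 is 390 + 33 = Day 423

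Discharge is Day 397 or later, so with discharge on schedule 3 central panels fall after it. The stay-local period ends at Day 14 (Day 403), so 2 of the 3 (Days 410 and 423) come after it. The central chemistry panel, with creatinine, is drawn at all 3. Local cystatin C at Visits 23 to 27 is done only when possible and lacks the same reference.

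**What the site does hold.** Cystatin C is sensitive only at Day 360. The clinical safety panel is drawn at Screening, repeatedly through Year 1 to Day 240, and centrally at Days 391 and 393 except in Japan. The last site-visible scheduled pre-dose central value is therefore 390 − 240 = 150 days before dosing, against 390 − 360 = 30 days for Visit 19. Boys delayed by a dosing pause have later clinical safety panels under Section 5.3.2 that are not on the withheld list. Section 8.2.10 names none of these values.

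**Creatinine.** It is neither on the Section 6.3.3 list nor in criterion 2 of Section 7.1, so its Visit 19 value should reach the site. The exception would be a reading of Section 7.1 in which chemistry profiles means the whole chemistry panel.

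**The case against.** The strongest reply is that the renal trigger still works. It is met by cystatin C or by creatinine, and creatinine is drawn at all three post-discharge panels. It asks for a clinically relevant increase, which is a judgement and does not fail for want of one number. Investigators must review every laboratory report and hold several earlier cystatin C values. All of this stands, and it keeps the point minor.

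A second reply is that Screening may serve in Year 2. The creatinine criteria for eculizumab in Section 6.5.1 use Screening with no split by year. Section 8.2.10 does the same for hematocrit, hemoglobin and haptoglobin, and its renal sentence is a chain of alternatives. That reading is possible but less natural, because the sentence gives Year 2 its own reference. If it was intended, the text should say so. Screening would by then be 390 + 30 = 420 to 390 + 90 = 480 days old.

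A third reply is that the handling may sit in the E-DMC charter, a laboratory manual or a monitoring plan. That cannot be excluded, but the protocol sections as they stand still conflict.

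In the other direction, a reader might infer that a site knows only the 1.2 x ULN eligibility ceiling, and so could be sure of a doubling only at 2 × 1.2 = 2.4 x ULN. The documents do not support this, because sites see cystatin C at Screening, through Year 1 to Day 240 and, outside Japan, just after dosing.

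**Conclusion.** The conflict is real and narrow. On the natural reading, the site cannot apply the cystatin C limb against its named reference in Year 2. This affects 1 of the 2 renal analytes, including at the 3 post-discharge central panels.

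A reader might infer that renal monitoring after Year 2 dosing fails. It does not. The creatinine limb and the urine output, anion gap, smear, haptoglobin and platelet triggers are intact. Cystatin C is not among the eculizumab criteria in Section 6.5.1. No dosing rule, treatment threshold or efficacy endpoint is affected.

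The conclusion rests on three assumptions: that Visit 19 is the only Year 2 reference for this bullet, that the withheld values are not released after the eligibility decision, and that Section 7.1 does not also hide creatinine. If the last fails, the problem extends to the Visit 19 reference for creatinine as well. The conflict lasts only while the study is blinded. The number of boys affected cannot be derived. The text at hand ends before the Japan appendix, which has its own intensified-monitoring section (10.10.4), so that section was not checked. Minor priority.

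**What to change.** Choose one of two wordings for the cystatin C reference:

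1. State in Sections 8.2.10 and 6.3.3 that, in Year 2, the unblinded medical monitor compares post-dose cystatin C with Visit 19 for both cohorts and alerts the site when the trigger is met. The monitor already holds the Visit 19 value. The added work is three scheduled central panels per dosed boy after discharge, plus the two inpatient panels outside Japan. Handling both cohorts alike keeps the blind.
2. Name a Year 2 reference the site can see, such as the last unblinded pre-dose central value (Day 240). This needs no extra review, but the reference is 150 days old at dosing instead of 30.

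In either case, state in Section 7.1 that the withheld Visit 19 profiles are only the analytes listed in Section 6.3.3, so that Visit 19 creatinine stays visible as the reference for central samples. The local pre-infusion creatinine at Visit 20 can then serve local samples. No threshold changes. The cost is protocol wording and, under the first option, a line in the monitoring plan.
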